### C.6.8.2 Secondary Endpoints Assessed for TAVI Only

The following secondary endpoints will be assessed for the TAVI cohort subjects only:

20. Device success defined as follows:

- Absence of procedural mortality AND
- Correct positioning of a single prosthetic heart valve into the proper anatomical location AND
- Intended performance of the prosthetic heart valve (no prosthesis-patient mismatch and mean aortic valve gradient <20 mmHg or peak velocity <3 m/s, AND no moderate or severe prosthetic valve regurgitation\*)
  - Assessed acutely in a resting state, either within 24-48 hours after the index procedure or before hospital discharge

\*Refers to VARC-2 definitions

Device success, as defined above, will be calculated for all subjects undergoing the TAVI procedure.

The endpoint is descriptive and no statistical hypothesis test will be performed.

21. Procedural success, defined as device success and absence of in-hospital MACCE.

Procedural success, as defined above, will be calculated for all randomized subjects undergoing the TAVI procedure.

The endpoint is descriptive and no statistical hypothesis test will be performed.

22. Evidence of prosthetic valve dysfunction at 30 days, 6 months, 12 months, 24 months, and annually thereafter up to 5 years.

The number of subjects with evidence of prosthetic valve dysfunction will be evaluated at 30 days, 6 months, 12 months, 18 months, 24 months, and annually thereafter up to 5 years. Point estimates and 95% BCIs for each time point will be presented using methods described below in the Bayesian version of a comparison of proportions (with predictions).

23. Resheath and Recapture (combined) success rate.

The success rate will be analyzed for all subjects in whom the resheath or recapture feature is attempted. The number and percentage of successful resheath or recapture attempts combined will be calculated. Separate resheathing and recapturing success rates will also be calculated.

The endpoint is descriptive and no statistical hypothesis test will be performed.

### C.6.9 Rationale for Selection of Trial Endpoints

Trial endpoints were selected with following considerations:

- Clinically relevant and address important safety and performance aspects of the investigational TAVI device
- Objectively defined and measurable in the majority of subjects
- Consistent with current recommendations for endpoints in TAVI clinical studies and VARC-2

### C.6.10 Multiplicity Considerations

It is recognized that with a multiplicity of tests comes inflation in the chance of a false finding of superiority or non-inferiority. Therefore, for the purpose of seeking approved labeling claims on designated secondary objectives, the following standard will be used: If the primary objective demonstrates non-inferiority, claims will be sought for selected secondary non-inferiority and superiority objectives and for superiority on the primary objective metric. These will be tested via a hierarchical (sequential) testing order that preserves the overall study-wise type I error rate at the level of 0.05, while requiring all non-inferiority tests to meet a nominal type I error rate of 0.05 and all superiority tests to meet a nominal type I error rate of 0.025. The testing order is specified below. The following objectives are tested in order, and testing continues if and only if all previous objectives have met their designated success criterion.

1. Primary endpoint (non-inferiority)

2. Transvalvular mean gradient at 12 months (non-inferiority)
3. Effective orifice area at 12 months (non-inferiority)
4. Change in NYHA classification from baseline to 12 months (non-inferiority)
5. Change in KCCQ score from baseline to 30 days (non-inferiority)

All of the above are non-inferiority tests and are tested with a type I error standard of 0.05. If all of the above tests meet their success criterion, the type I error rate of 0.05 that is passed on from the above tests will be split equally (using a Bonferroni justification) between the following parallel subfamilies, so that each subfamily is tested using a type I error rate of 0.025:

Subfamily #1: Primary endpoint (superiority)

Subfamily #2: Secondary (superiority) objectives #5–#18 as enumerated below, tested in ordered sequence such that all  $\alpha$  is passed on to subsequent tests if a test criterion is met, while all testing stops if a test criterion is not met. This procedure controls the type I error rate of this subfamily at the level 0.025.

It is not necessary to “pass” all objectives in one subfamily in order to test the objective(s) in the other subfamily. For the purposes of seeking claims, these objectives will only be evaluated once, at the same time as non-inferiority of the primary objective is established. The only exception to this is the primary endpoint superiority test, which carries the possibility of a delayed determination of superiority (as described in Section 4.2.1) and may thus meet its success criterion at a different time.

The remaining secondary objectives may be of interest for scientific or financial reasons but will not be the basis for supporting labeling claims; they are thus outside of the hierarchical testing procedure. Similarly, for those objectives that test non-inferiority, if non-inferiority is established, a test of superiority will also be conducted, but unless specifically itemized in the list, such superiority testing is not part of the hierarchical testing procedure; these superiority tests may be of interest for scientific or financial reasons but will not be the basis for supporting labeling claims.

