Physicians' preferences for lesser invasive strategies have fuelled the ongoing interest in developing minimally invasive transcatheter therapies. Alain Cribier pioneered the transcatheter aortic valve implantation (TAVI) technology and reported the first-in-man experience of TAVI in a patient with symptomatic AS who was deemed inoperable in 2002(10). Subsequent feasibility studies validated the proof of concept (11, 12). The Edwards-SAPIEN valve (Edwards Lifesciences, Irvine, CA, USA) and the Medtronic CoreValve system (Medtronic Corporation, Minneapolis, MN, USA) were the first two TAVI platforms with CE mark approval, followed by the Symetis Acurate (Symetis, Ecublens, Switzerland) and JenaValve (JenaValve, Munich, Germany). Numerous single-center and multi-center observational registries followed suggesting the safety and performance of the TAVI technology (13-17). The TAVI technology comes with its own specific complications (18), not necessarily overlapping with those of SAVR: vascular injury; stroke, cardiac injury such as heart block, coronary obstruction, and cardiac perforation; paravalvular leak; and valve misplacement. The non-uniformity in presenting respective data makes a comparison of results from different centers challenging (19, 20). The Valvular Academic Research Consortium (VARC), a FDA-endorsed collaboration between academic research organizations and professional societies in the United States and Europe is an initiative to generate a consensus statement on TAVI related definitions aiming to create order and uniformity making data more prone to analysis and comparison (21, 22).

Technical refinements and commercial entrepreneurship have made the technology accessible to many centers worldwide. This might pose future implications since few randomized trials with TAVI have been performed.

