#### Sample Size Justification

The assumed values  $\pi_T = \pi_C = 0.17$  are based on the data published by Iturra et al and CoreValve US Pivotal High Risk study results. As reported in the Iturra paper, the incidence of all-cause mortality at 30 days was 2.8% and the late all-cause mortality Kaplan-Meier rate at 24 months was 12.1%. The overall 24-month all-cause mortality rate was approximately 15%. STS score reported in the Iturra paper ( $5.6 \pm 1.1$ , n=502) was similar to the STS score for subjects currently enrolled in the SURTAVI study ( $5.6 \pm 1.4$ , n=654), and it is believed that the 24-month all-cause mortality rate in SURTAVI will be approximately 15% at 24 months. The major stroke rate was 3.2% for subjects who survived to 1 year in the CoreValve Pivotal High Risk study. The High Risk study enrolled a higher-risk population than SURTAVI, therefore, the major stroke rate in the High Risk study is adjusted downward, and it is believed the disabling stroke rate at 24 months would be approximately 2% in the SURTAVI study. Overall, the estimation of the all-cause mortality or disabling stroke rate at 24 months is 17%.

Although the pre-specified analysis methods are Bayesian, the sample size is guided by a standard frequentist non-inferiority power analysis. Under the assumptions of  $\pi_T = \pi_C = 0.17$ , non-inferiority margin  $\delta=0.07$ , 1:1 randomization,  $\alpha= 0.05$ , and power = 95%, the method of Farrington and Manning as implemented in PASS 2008 indicates that the required sample size for a single-look analysis is 1258. To allow for up to 6% dropout, 1339 subjects must be accrued. Furthermore, to compensate for power lost in a two-look group sequential analysis plan using Pocock-type alpha spending, the sample size would have to be increased by about 12.5%. This leads to an estimated sample size of 1531. Thus a sample size of 1600 mITT subjects should provide ample power for establishing non-inferiority in the primary hypothesis test.

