#### Analysis Plan

An interim analysis (timed to occur when 1400 mITT subjects have reached 12 months) for the purpose of declaring an early win will be conducted. At this analysis,  $\Pr(H_{\delta=0.07} | \text{data}) > \Psi$ ,

 Medtronic CoreValve SURTAVI Trial 2014 FDA Annual Progress Report;

 Farrington, C. P. and Manning, G. 1990. 'Test Statistics and Sample Size Formulae for Comparative Binomial Trials with Null

 Hintze, J. (2004). NCSS and PASS, Number Cruncher Statistical Systems. Kaysville UT. www.ncss.com

 Jennison C and Turnbull BW, Group Sequential Methods with Applications to Clinical Trials. Boca Raton: Chapman & Hall, 2000, p 27

non-inferiority will be declared at this time, and a regulatory submission will follow. Alternatively, if  $P(H_{\delta=0.07} | \text{data}) \leq \Psi$ , all mITT subjects will be followed to 24 months, when a final analysis will occur. At the final analysis, the standard for trial success will again be  $P(H_{\delta=0.07} | \text{data}) > \Psi$ . These two analyses are termed "Win Looks."

If, at the early (interim) "Win Look," non-inferiority is established, a test of superiority will immediately follow. If  $P(H_{\delta=0} | \text{data}) > \Psi_{\text{SUP}}$ , superiority will be established at this time. However, if  $P(H_{\delta=0} | \text{data}) \leq \Psi_{\text{SUP}}$ , subjects will continue to be followed and analyzed according to the same analysis plan. At the final "Win" analysis, if  $P(H_{\delta=0} | \text{data}) > \Psi_{\text{SUP}}$ , a delayed determination of superiority will be made.

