where  $\mu_{TAVI}$  and  $\mu_{SAVR}$  denote the mean improvements in the KCCQ score from baseline to 30 days. For subjects with KCCQ score at both baseline and 30 days, the improvement in KCCQ will be calculated as  $KCCQ_{30day} - KCCQ_{baseline}$ . This objective will be evaluated using a Bayesian version of a two-sample t-test (see Section C.11). The posterior probability  $P(H | data)$  will be calculated and compared to a threshold of 0.975.

9. Days alive out of the hospital at 12 months after TAVI vs. SAVR (secondary objective #10). The hypothesis of interest is

$$H: \mu_{TAVI} > \mu_{SAVR}$$

where  $\mu_{TAVI}$  and  $\mu_{SAVR}$  denote the mean number of days alive out of the hospital at 12 months. This objective will be evaluated using a Bayesian version of a two-sample t-test (see Section C.11). The posterior probability  $P(H | data)$  will be calculated and compared to a threshold of 0.975.

10. Days alive out of the hospital at 24 months after TAVI vs. SAVR (secondary objective #10). The hypothesis of interest is

$$H: \mu_{TAVI} > \mu_{SAVR}$$

where  $\mu_{TAVI}$  and  $\mu_{SAVR}$  denote the mean number of days alive out of the hospital at 24 months. This objective will be evaluated using a Bayesian version of a two-sample t-test (see Section C.11). The posterior probability  $P(H | \text{data})$  will be calculated and compared to a threshold of 0.975.

11. Change in SF-36 Physical Summary Scale from baseline to 3 months: TAVI vs. SAVR (secondary objective #11). The hypothesis of interest is

$$H: \mu_{TAVI} > \mu_{SAVR}$$

where  $\mu_{TAVI}$  and  $\mu_{SAVR}$  denote the mean improvements in the SF-36 Physical Summary Scale from baseline to 3 months. This objective will be evaluated using a Bayesian version of a two-sample t-test (see Section C.11). The posterior probability  $P(H | \text{data})$  will be calculated and compared to a threshold of 0.975.

12. Change in EQ-5D from baseline to 3 months: TAVI vs. SAVR (secondary objective #11). The hypothesis of interest is

$$H: \mu_{TAVI} > \mu_{SAVR}$$

where  $\mu_{TAVI}$  and  $\mu_{SAVR}$  denote the mean improvements in the EQ-5D from baseline to 3 months. This objective will be evaluated using a Bayesian version of a two-sample t-test (see Section C.11). The posterior probability  $P(H | \text{data})$  will be calculated and compared to a threshold of 0.975.

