13. Incidence of MACCE at 30 days or hospital discharge, whichever is longer: TAVI vs. SAVR (secondary objective #1). The hypothesis of interest is

$$H: \pi_{TAVI} < \pi_{SAVR}$$

where  $\pi_{TAVI}$  and  $\pi_{SAVR}$  denote the binary rate of MACCE at 30 days or hospital discharge (if longer). The posterior probability  $P(H | \text{data})$  will be calculated and compared to a threshold of 0.975. The statistical method will be the Bayesian version of a comparison of proportions (see Section C.11).

14. Incidence of major vascular complications at 30 days or hospital discharge, whichever is longer: TAVI vs. SAVR (secondary objective #3). The hypothesis of interest is

$$H: \pi_{TAVI} < \pi_{SAVR}$$

where  $\pi_{TAVI}$  and  $\pi_{SAVR}$  denote the binary rate of major vascular complications at 30 days or hospital discharge (if longer). The posterior probability  $P(H | \text{data})$  will be calculated and compared to a threshold of 0.975. The statistical method will be the Bayesian version of a comparison of proportions (see Section C.11).

15. Incidence of major or life-threatening bleeding event at 30 days or hospital discharge, whichever is longer: TAVI vs. SAVR (secondary objective #3). The hypothesis of interest is

$$H: \pi_{TAVI} < \pi_{SAVR}$$

where  $\pi_{TAVI}$  and  $\pi_{SAVR}$  denote the binary rate of major or life-threatening bleeding events at 30 days or hospital discharge (if longer). The posterior probability  $P(H | \text{data})$  will be calculated and compared to a threshold of 0.975. The statistical method will be the Bayesian version of a comparison of proportions (see Section C.11).

16. Incidence of all strokes at 30 days or hospital discharge, whichever is longer: TAVI vs. SAVR (secondary objective #15). The hypothesis of interest is

$$H: \pi_{TAVI} < \pi_{SAVR}$$

where  $\pi_{TAVI}$  and  $\pi_{SAVR}$  denote the binary rate of strokes at 30 days or hospital discharge (if longer). The posterior probability  $P(H | \text{data})$  will be calculated and compared to a threshold of 0.975. The statistical method will be the Bayesian version of a comparison of proportions (see Section C.11).

17. Incidence of moderate/severe aortic insufficiency after TAVI vs. SAVR (secondary objective #12). The hypothesis of interest is

$$H: \pi_{TAVI} < \pi_{SAVR}$$

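### After an early win, the 24-month days-alive-out-of-hospital claim gets its only test at a look timed on 12-month follow-up, and failing it closes eight later claims measured by 3 months

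*Combined protocol and SAP*

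**What the plan says.** Four provisions have to be read together.

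- **Interim look** (Analysis Plan under C.6.5.2): "An interim analysis (timed to occur when 1400 mITT subjects have reached 12 months" is planned so that an early win can be declared. If the posterior threshold is not met, all mITT subjects are followed to 24 months and a final analysis is done.
- **One evaluation** (C.6.10): for the purpose of claims, "these objectives will only be evaluated once, at the same time as non-inferiority of the primary objective is established". Superiority on the primary endpoint is the single exception; it may be determined later.
- **Stop rule** (C.6.10): Subfamily #2 holds claims 5 to 18 of C.6.10.1 in fixed order at 0.025. All alpha passes on after a success, "while all testing stops if a test criterion is not met".
- **Claim 10** (C.6.10.1): "Days alive out of the hospital at 24 months after TAVI vs. SAVR (secondary objective #10"). It compares mean numbers of days with a Bayesian two-sample t-test against a posterior threshold of 0.975.

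The claims behind it are SF-36 and EQ-5D change at 3 months (11, 12); MACCE, major vascular complications, major or life-threatening bleeding and all strokes at 30 days or discharge (13 to 16); aortic insufficiency at the discharge echo (17); and the new pacemaker rate at 30 days or discharge (18).

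**The concern.** The look that triggers the claims is timed on 12-month follow-up, but one link in the chain needs 24 months. If non-inferiority is declared early, claim 10 must be tested while a large share of subjects have not reached its time point, and it cannot be tested for a claim again. Claims 11 to 18 can then be lost because of the immaturity of an unrelated endpoint, although their own assessment times have passed.

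The text reviewed does not say how unfinished follow-up enters the test. In C.6.8 the predictive version of the method is attached only to comparisons of proportions. For days alive out of hospital the plan names only a Bayesian t-test. Counting subjects with 12 to 23 months as they stand cuts their day totals short for administrative reasons; leaving them out discards nearly half the sample, and those kept are the earliest enrolled.

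**Working it through.** **The plan's own sample size first** (Sample Size Justification). Inputs: 0.17 in both arms, margin 0.07, alpha 0.05 one-sided, power 95%, "1:1 randomization".

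- Farrington-Manning: the restricted rates that differ by 0.07 are 0.2105 and 0.1405. s0 = √(0.2105×0.7895 + 0.1405×0.8595) = 0.5357; s1 = √(2×0.17×0.83) = 0.5312.
- n per arm = [1.645×(0.5357 + 0.5312)/0.07]² = 628.6, so 629×2 = 1258. This matches the plan.
- Dropout: 1258/0.94 = 1338.3, so 1339, as in "To allow for up to 6% dropout, 1339 subjects must be accrued". Two looks: 1339/0.875 = 1530.3, so 1531. Both match.

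**Follow-up at the interim.** Inputs: 1600 mITT subjects (C.6.5.2), about 36 months of enrollment (C.3.5), interim 12 months after the 1400th subject. Uniform accrual is an assumption.

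- The 1400th subject enters at 36×1400/1600 = 31.5 months; the interim falls at 31.5 + 12 = 43.5 months.
- Subjects with 24 months: (43.5 − 24)/36×1600 = 867, or 54%.
- Accrual over 24 months: interim at 33, (33 − 24)/24×1600 = 600 (38%). Over 48 months: interim at 54, (54 − 24)/48×1600 = 1000 (63%).
- Back- to front-loaded accrual over 36 months gives 580 (36%) to 956 (60%).
- By contrast, 1400/1600 = 87.5% have reached 12 months, and the last subject entered has 43.5 − 36 = 7.5 months (9 and 6 months for 24 and 48 months' accrual). Every subject is therefore past the assessment times of claims 11 to 18.

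**Chance that the interim is where claim 10 is tested.** True rates 0.17 in both arms, threshold 0.971 (normal equivalent 1.896), 1600×0.94/2 = 752 evaluable per arm.

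- Drift at full information: 0.07/√(2×0.17×0.83/752) = 3.61.
- P(win) = Φ(3.61√t − 1.896): 0.78 at information fraction t = 0.54, and 0.89 at t = 0.75 (an assumed value that credits partial follow-up).
- Simulation with Beta(1,1) priors: 0.80 with 433 completers per arm; 0.86 to 0.90 when subjects at 12 months are predicted forward (assumed 12-month rate 0.09 to 0.13). The ceiling is 0.945 if all 1400 had 24-month data.

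This gives roughly 80-90%.

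**Cost to claim 10, as an illustration.** The documents give no effect size, standard deviation or power for this endpoint, so the starting power is hypothetical. With completers only, the standard error grows by 1/√0.542 = 1.36. Power at fraction f is Φ((1.96 + z)√f − 1.96), where z is the normal quantile of the full-data power.

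| Full-data power | f = 0.54 |
|---|---|
| 80% | 54% |
| 90% | 66% |
| 95% | 75% |

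For 90%, the range is 51% at f = 0.375 to 73% at f = 0.625.

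**The case against.** The strongest reply is that nothing central is touched. Primary non-inferiority, primary superiority (its own subfamily, with delayed determination), type I error and subject safety all stand. The loss is one of power for sponsor claims, and it arises only if the interim wins. That is correct, and it limits how serious the point is.

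The 66% is hypothetical and unconditional. Claim 10 is reached only after claims 5 (length of stay) and 9 (12-month days alive out of hospital) have passed. Both overlap with it, because the implant hospitalization counts. Power given those passes was not computed. This stands, and the figure is offered only as an illustration.

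Section C.11, where the t-test is described, and the detailed SAP are not in the part reviewed and may hold a rule for partial follow-up. For the ratio form of the endpoint, C.6.8.1 counts days alive to the last follow-up date, so partial follow-up is contemplated there. Such a rule could narrow the data gap. It would not change when claim 10 is tested or what its failure stops.

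A reader might also infer that claims 14, "Incidence of major vascular complications at 30 days or hospital discharge, whichever is longer: TAVI vs. SAVR (secondary objective #3"), and 17 are misplaced, because B.1 lists TAVI complications as "not necessarily overlapping with those of SAVR: vascular injury; stroke, cardiac injury such as heart block, coronary obstruction, and cardiac perforation; paravalvular leak". The documents do not support this. The same sentence names stroke and heart block, which are the subjects of claims 16 and 18, so it gives no reason to put 14 and 17 behind them. Neither has a timing problem, and any fixed order controls error.

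**Conclusion.** The point holds for claim 10 and should be fixed. It rests on the plan's single-evaluation and stop rules, an interim timed on 12-month follow-up, and an 80-90% chance of winning there under the plan's assumptions. At that look about 54% of subjects would have 24-month data (38-63% for uniform accrual over 24 to 48 months), with eight claims waiting behind the test.

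Three stronger readings go too far. The 24-month data would be incomplete, not absent, and C.6.8.1 still plans a 24-month comparison outside the claims. The plan does not itself call an early win expected; that follows from its assumptions. And claims 11 to 18 are past their assessment times but not necessarily complete: 3-month SF-36 is collected in five countries only, and questionnaires may be missing where no translation exists (R.12). If non-inferiority is reached only at the final look, the problem does not arise.

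**What to change.** Before any unblinded look, move claim 10 to the last position in Subfamily #2, after claim 18, so that it gates nothing. Claim 9 already tests the 12-month version earlier in the sequence. A pre-specified fixed order keeps the subfamily error at 0.025.

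Optionally, let claim 10 be decided once, when 24-month follow-up is complete, but only if claims 5 to 9 and 11 to 18 have all passed. That still preserves 0.025. It should not run in parallel with claims 11 to 18 at the full 0.025: the bound would then be 0.025 + 0.025 = 0.05 (1 − 0.975² = 0.049 if independent). Whichever option is chosen, state how incomplete follow-up enters the days-alive t-test, or point to where this is already stated.

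The wording change is a few lines in C.6.10 and C.6.10.1 and the matching SAP text. It is still an amendment to an open-label trial analyzed by the sponsor's statistics department, and the change history records earlier statistical changes as made by agreement with FDA. The reason and date should therefore be documented. The price is that claim 10 is reached only if all the others pass, or is decided later.

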The statistical approach for these analyses is Bayesian. The prior distributions for  $\pi_T$  and  $\pi_C$  in these calculations are Beta (1,1). The threshold  $\Psi$  is designated to be 0.971 for non-inferiority testing and  $\Psi_{\text{SUP}} = 0.989$  for superiority testing; these values are selected by trial-and-error to achieve a type I error (under simulation) of at most 0.05 for non-inferiority testing and at most 0.025 for superiority testing. Of note, establishing  $P(H_{\delta=0} | \text{data}) > \Psi_{\text{SUP}}$  means that superiority has been established to a standard equivalent to a nominal significance level of 0.025 (1-sided), but this does not automatically mean that a labeling claim of superiority is supported. See "Multiplicity Considerations" (Section C.12) for additional requirements regarding labeling claims on secondary objectives.

Further details of planned analyses are provided in the SAP.

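### Claim 10 (days alive out of hospital at 24 months) is tested at a fixed 0.975 at whichever look the primary first passes, so the stated 0.025 for its subfamily is not guaranteed; the worst case is about 0.026 to 0.030.

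*Combined protocol and SAP*

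**What the plan says.** C.6.10 describes a fixed testing order that "preserves the overall study-wise type I error rate at the level of 0.05". For subfamily #2, the superiority claims numbered 5 to 18 in C.6.10.1, it adds: "This procedure controls the type I error rate of this subfamily at the level 0.025". On timing it says that "these objectives will only be evaluated once, at the same time as non-inferiority of the primary objective is established"; only superiority on the primary endpoint may be determined later.

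The Analysis Plan under C.6.5.2 gives the primary two looks. The first is "timed to occur when 1400 mITT subjects have reached 12 months" and the second is when all subjects have been followed to 24 months. For the primary, the thresholds are raised to allow for both looks: 0.971 for non-inferiority and 0.989 for superiority, chosen to give a "type I error (under simulation) of at most 0.05 for non-inferiority testing and at most 0.025 for superiority testing".

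The secondary claims have no such adjustment. C.6.10.1 sets 0.95 for the non-inferiority claims and 0.975 for the superiority claims, whichever look applies. Claim 10 compares arm means that "denote the mean number of days alive out of the hospital at 24 months", at 0.975.

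**The concern.** A test that is done once is not the same as a test done at a fixed time. Here the primary data choose the look. If a secondary statistic is correlated with the primary and its data are still accruing at the interim, some trial paths lead to a full-level test on the interim data and others to a full-level test on the final data. The rejection probabilities of the two sets of paths add up, and nothing in the design holds their sum to the nominal level. The fixed sequence and the Bonferroni split justify how alpha moves between hypotheses. They do not address when each is tested.

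Claim 10 is the exposed case. It is a 24-month measure read at an interim timed on 12-month follow-up. It also depends on death, which on the plan's own figures accounts for about 15 of the 17 percentage points of the primary event rate. At stake is a stated error property behind a labeling claim, not the primary conclusion.

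**Working it through.** **Inputs from the plan.** 1600 mITT subjects, 1:1; enrolment about 36 months (C.3.5); interim when 1400 have reached 12 months; primary rate 0.17 in both arms, margin 0.07; primary threshold 0.971 (z = 1.896); claim 10 threshold 0.975 (z = 1.960).

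**Assumptions.** Uniform accrual, and the correlation ρ between the claim 10 and primary statistics. The plan gives neither. An illustrative model built on the plan's 15% mortality put ρ at 0.76 to 0.80; I show 0.3 to 0.9.

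**Plan's own figure first.** For a threshold z-value c used at both looks, with interim information fraction t, the two-look error is 1 − Φ₂(c, c; √t). At t = 0.54 this gives 0.0471 for 0.971 and 0.0186 for 0.989. Both lie inside the stated limits of 0.05 and 0.025.

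**Interim information.**
- 1400 subjects are enrolled by 36 × 1400/1600 = 31.5 months, so the interim falls at 43.5 months.
- 24-month data exist for those enrolled by 19.5 months: 19.5/36 × 1600 ≈ 867, so t = 0.54.
- 12-month claims: 1400/1600 = 0.875.
- The last subject enrolled has 43.5 − 36 = 7.5 months of follow-up, so the discharge, 30-day and 3-month claims are complete at both looks.

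**Error of claim 10, taking claims 1 to 9 as passed.** With P for the primary and S for claim 10:

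error = Pr(P₁ > 1.896, S₁ > 1.960) + Pr(P₁ ≤ 1.896, P₂ > 1.896, S₂ > 1.960)

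S has no true effect, and the error is maximised over the true primary difference. The standard error of that difference is √(2 × 0.17 × 0.83/800) = 0.0188. Equal rates therefore give a final drift of 0.07/0.0188 = 3.73, and a drift d corresponds to a TAVI excess of 0.07 − 0.0188d.

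Primary and claim 10 both at 0.54:

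| ρ | Maximum error | TAVI excess at the maximum | Error at equal rates |
|---|---|---|---|
| 0.3 | 0.0258 | 0.9 points | 0.0256 |
| 0.5 | 0.0269 | 2.5 points | 0.0256 |
| 0.7 | 0.0287 | 4.1 points | 0.0252 |
| 0.8 | 0.0303 | 4.8 points | 0.0251 |
| 0.9 | 0.0328 | 5.7 points | 0.0250 |

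A 4-million-draw simulation near the ρ = 0.8 maximum gives 0.0302.

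**Dependence on the primary's interim information** (claim 10 at 0.54, ρ = 0.8): 0.0303 at 0.54, 0.0281 at 0.60, 0.0255 at 0.70, 0.0250 at 0.80.

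**Dependence on accrual** (ρ = 0.8, both endpoints at the same fraction): 0.0335 if accrual takes 24 months (t = 0.375), 0.0288 if it takes 48 months (t = 0.625).

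**Effect of the gate.** Simulated at drift 1.2 with correlations of 0.8 (primary, claim 10), 0.6 (primary, claim 9) and 0.9 (claims 9, 10). When claim 9 has a final drift of 0, 1 or 2, the error of claim 10 is 0.012, 0.026 or 0.030.

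**12-month claims.** For ρ up to 0.5 the maximum is 0.0504 against 0.05 and 0.0252 against 0.025. At ρ = 0.7 it is 0.0510 and 0.0256.

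**Study-wise level.** Adding the maximum for primary superiority and the ρ = 0.8 maximum for claim 10 gives 0.0186 + 0.0303 = 0.0489, below 0.05. The two maxima do not occur together: at equal rates, where the 0.0186 arises, the sum is 0.0186 + 0.0251 = 0.0437.

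**The case against.** The strongest reply is that the excess needs several conditions at once: the primary's interim information near 0.54, a high correlation, TAVI truly worse on the primary by an amount still inside the margin, and claims 1 to 9 almost sure to pass. The first is open to doubt. The interim is timed on 12-month follow-up for a 24-month endpoint, and C.6.8 uses comparisons of proportions with predictions for other endpoints. If the primary is handled in the same way, its interim information could exceed the completers' 54%, and at 0.80 the excess is gone. The pages I have leave the detail to SAP sections that I have not seen, including the cited 4.2.1 and C.11. Claim 9, the same measure at 12 months, is also a real filter.

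All of that stands, and it limits the size. It does not rescue the statement as written. Control at 0.025 has to hold for every primary effect, including unfavourable ones within the margin, and the plan offers no argument that it does.

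A reader might infer that every claim with incomplete interim data (1 to 3, 6, 7, 9 and 10) is materially affected. The documents do not support that. The NYHA claim uses only subjects with both visits and the echo claims only subjects who have the echo, so deaths before 12 months contribute nothing to them and a high correlation with the primary has no basis. The 12-month excess is negligible at correlations of 0.5 or below. Nor does a secondary claim get two attempts: if the primary misses at the interim, the claim is not tested there.

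**Conclusion.** The concern holds for claim 10 and is minor. The stated control of subfamily #2 at 0.025 is not guaranteed. With 54% interim information for both endpoints and claims 1 to 9 nearly certain to pass, the maximum is 0.026 to 0.030 for correlations of 0.3 to 0.8, and 0.033 at 0.9. These are worst cases and not expected values. At 0.7 to 0.8 they need TAVI truly about 4 to 5 points worse on the primary; at the planned equal rates the error is about 0.025.

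A reader might also infer that the study-wise 0.05 fails. Claim 10 alone does not breach it, as the sum above shows. The figures rest on assumed accrual, correlation and primary interim information, none of which the documents supply.

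**What to change.** Change claim 10 only and leave every other threshold as it is. Either of these will do, if made before the interim:

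- **Two-look threshold for claim 10.** The plan's own 0.989 at both looks caps the error at 0.0186 for t = 0.54, whatever the correlation. That is stricter than needed. A milder value calibrated to 0.025 is enough: by the same two-look formula, 0.986 (z = 2.197) at t = 0.54 gives 0.0235. The value should be set for the interim fraction actually expected.
- **Keep 0.975 and correct the wording.** In C.6.10, replace the statement that subfamily #2 is controlled at 0.025 with the achieved maximum error and the assumptions behind it.

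The first option costs power. A claim with 80% power at 0.975 has Φ(1.960 + 0.842 − 2.290) = Φ(0.512), about 70%, at 0.989. Because testing is sequential, part of that loss passes to claims 11 to 18. Raising the thresholds of the 12-month claims as well would be out of proportion: claims 1 to 3 gate everything after them, and their excess is negligible. The second option costs only wording. Neither needs new data, visits or subjects.
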